## 9. RISK BENEFIT ASSESSMENT

### 9.1 Known Potential Risks

- A. Loss of confidentiality/privacy is a risk in all studies collecting personal and/or sensitive data.
- B. The only anticipated adverse event (AE) related to the 12-lead ECG is skin irritation or discomfort associated with the electrodes. It is possible the 12-lead ECG may uncover a medical condition in which the participant was previously unaware. This is considered an incidental finding. Refer to Section 8.4 for handling
- C. During blood pressure monitoring, some participants may feel some discomfort as the blood pressure cuff loosens and tightens during the assessment.
- D. There are no associated adverse events with pulse oximetry monitoring.

### 9.2 Risk Mitigation

- A. Efforts to protect participant confidentiality are described in section 11.2.4. Privacy breaches will be reported to the relevant participant/s and will be treated as an unanticipated problem despite being listed here (see Sections 8.7 and 11.2.4)
- B. Participants reporting a history of allergic reactions to medical adhesives will not be recruited.

Participants will be monitored by study staff during the study procedure, if at any point the participant wants to stop, the study will be stopped, and the participant may withdraw from the study.

### 9.3 Known Potential Benefits

Participation in this study will not result in direct benefit to the participant.

Document ID:	CC_TC_ECR_Intrepid 12Lead_2022_11549	Document title: Philips HeartStart Intrepid 12-lead ECG Study – The ICE study Protocol	Classification:	For internal use
Modified:	12SEP2022	Clinical Protocol	Author:	[name]
Version:	2.0		Approver:	Ref to Page 2
Status:	Final		Page:	40 of 51

## 9.4 Assessment of Potential Risks and Benefits

It is the opinion of the Sponsor and the Principal Investigator that the benefits of this protocol outweigh the risks.

## 10. STATISTICAL CONSIDERATIONS

The statistical analysis plan has been incorporated into this protocol. It is not a stand-alone document.

### 10.1 Sample Size Determination

Each hypothesized endpoint estimates a target proportion of 99% with an expectation to be statistically better than 90%. Using a one-sided exact test, with 80% power and alpha of 0.025, a sample size of 56 evaluable subjects is required.

Both hypothesized endpoints must be met for study success, therefore alpha level adjustments are not necessary to address familywise error.

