### 4.3 Sample size

Up to 60 (sixty) participants will be enrolled, for 56 (fifty-six) participants to complete data collection.

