### 10.2 General Considerations

Continuous data will be presented by mean, standard deviation, median, minimum and maximum observation, and 95% confidence interval. Categorical data will be presented as frequencies, percentages, and the 95% Clopper-Pearson confidence interval. Significance tests will be conducted at a two-sided significance level (alpha) of 0.05, or a one-sided significance level of 0.025.

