### 10.4.2 Analysis of the Primary Endpoints

Endpoint 1A: Obtaining the 12-lead ECG

Endpoint 1B: Diagnostic quality of the 12-lead ECG tracings

A one-sided exact binomial test will be used to assess each of the primary endpoints. Both endpoints must be met for study success.

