#### 11.1.3 Impact of Early Termination on Recruitment and Enrollment

Recruitment and enrollment will continue until 60 participants complete all study procedures.

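### Section 10.1 credits an exact test with normal-approximation figures: exact power at 56 is 89.2% per endpoint, 54 would suffice for 80%, and no power is given for the both-endpoints rule

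*Combined protocol and SAP*

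**What the plan says.** Section 10.1 sets a target of 99% against a bound of 90% for each endpoint and concludes: "Using a one-sided exact test, with 80% power and alpha of 0.025, a sample size of 56 evaluable subjects is required". Section 10.4.2 plans the same kind of test for the analysis: "A one-sided exact binomial test will be used to assess each of the primary endpoints". The one-sided level of 0.025 is repeated in Section 10.2.

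Section 10.4.2 adds: "Both endpoints must be met for study success". Sections 10.1 and 10.4.3 draw one consequence from this rule: "Both hypothesized endpoints must be met for study success, therefore alpha level adjustments are not necessary to address familywise error". They do not mention its effect on power. No pass mark, formula or software is given for the calculation.

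On numbers, Section 4.3 says: "Up to 60 (sixty) participants will be enrolled, for 56 (fifty-six) participants to complete data collection". Section 11.1.3 says: "Recruitment and enrollment will continue until 60 participants complete all study procedures".

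**The concern.** Every input to the calculation is printed, so the figure can be checked without outside assumptions, and the check does not return 56 at 80%. The only power figure in the plan is therefore not the power of the test it names. It is also a per-endpoint figure, whereas the trial succeeds only if two such tests both pass.

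The practical loss is that the plan hides how the exact test behaves. The normal approximation suggests that power changes smoothly with sample size. The exact rule moves in steps: it tolerates a whole number of failures, and that number changes abruptly at particular sizes. A reader of 10.1 cannot tell that the result turns on whether there is one failure or two, or that the tolerance disappears three subjects below the planned size.

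**Working it through.** **Inputs.** Null proportion 0.90, target 0.99, one-sided alpha 0.025, power 80%, 56 evaluable subjects (Section 10.1); exact binomial test (Section 10.4.2); both endpoints required (Sections 10.1, 10.4.2 and 10.4.3).

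**Step 1: reproduce the plan's figure.** The one-sample normal approximation, with the null variance for alpha and the alternative variance for power, is

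n = [(1.960 × √(0.90 × 0.10) + 0.842 × √(0.99 × 0.01)) / (0.99 − 0.90)]² = [(1.960 × 0.300 + 0.842 × 0.0995) / 0.09]² = 55.7, rounded up to 56.

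Approximate power at 56 is 80.5%. Both printed figures are recovered, but by a method other than the one named.

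**Step 2: the exact test at 56.** Find the smallest pass mark c with P(X ≥ c | 56, 0.90) ≤ 0.025.

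- P(X ≥ 55 | 56, 0.90) = 0.90^56 + 56 × 0.10 × 0.90^55 = 0.0027 + 0.0170 = 0.0198, so c = 55.
- Power = 0.99^56 + 56 × 0.01 × 0.99^55 = 0.5696 + 0.3222 = 0.8918.

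**Step 3: the exact test at other sizes.**

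| Evaluable | Failures allowed | Attained alpha | Power per endpoint |
|---|---|---|---|
| 53 | 0 | 0.0038 | 58.7% |
| 54 | 1 | 0.0237 | 89.8% |
| 55 | 1 | 0.0216 | 89.5% |
| 56 | 1 | 0.0198 | 89.2% |
| 60 | 1 | 0.0138 | 87.9% |
| 69 | 1 | 0.0060 | 84.8% |
| 70 | 2 | 0.0242 | 96.7% |

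At 53, one failure would give an attained alpha of 0.0259, just above 0.025, so none is allowed. The smallest size with at least 80% power is 54. From 54 to 69 the allowance stays at one failure, so power falls slowly as subjects are added.

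**Step 4: power for both endpoints at 56.** Both endpoints are measured on the same participants. Assume participants are independent, each endpoint has a true rate of 99%, and a participant fails both endpoints with probability q. Then each endpoint alone is failed with probability 0.01 − q, and neither with s = 0.98 + q. Both tests pass if each endpoint has at most one failure:

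P = s^56 + 56 × s^55 × [q + 2(0.01 − q)] + 56 × 55 × s^54 × (0.01 − q)²

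- Failures never coincide (q = 0): 0.3226 + 0.3687 + 0.1035 = 79.47%.
- Independent (q = 0.0001): 0.8918² = 79.53%.
- Half coincide (q = 0.005): 82.9%.
- All coincide (q = 0.01): 0.8918, or 89.2%.

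The range is 79.5% to 89.2%.

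**The case against.** The strongest reply is that nothing is harmed. The 80% is a planning target, 56 meets it with room to spare, and no size near 56 has exactly 80% power because exact binomial power moves in steps. This stands as far as it goes: the sample size is adequate, type I error is controlled, and a difference of two subjects is trivial. It does not rescue the sentence. If 80% means at least 80%, then 54 is the required size. If it were meant as joint power, independence gives 80.7% at 54, 80.1% at 55 and 79.5% at 56, so 56 would not be the answer there either.

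Four stronger readings are tempting, and the documents do not support them.

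- A reader might infer that the trial is underpowered. Per endpoint it exceeds its target, and joint power at the plan's own 99% is about 80% or higher. If an unobtained ECG also counts as a failure of diagnostic quality, failures overlap and joint power moves towards 89.2%.
- A reader might take the general lower bound for two events, 2 × 0.892 − 1 = 78.4%. That bound ignores that both endpoints come from the same 56 participants. The lowest attainable value is 79.5%.
- A reader might apply 99% for diagnostic quality only to ECGs that were obtained, which makes the overall rate 0.99 × 0.99 = 98.01% and leads to a joint power of 69.3%. Sections 3.2 and 10.1 set 99% for each endpoint, so this replaces the plan's assumption.
- A reader might expect the number evaluable to fall to 53. Under the cap of 60 in Section 4.3 that takes seven losses. Section 5.4 counts everyone who consents as enrolled, including later screen failures, and Section 10.7 rules out imputation, so losses are possible. But no loss rate is given, Section 5.5 considers drop-out unlikely, and Section 11.1.3 continues recruitment. The step is a boundary worth stating, not a forecast.

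**Conclusion.** The stated power and the stated required size are both wrong for the named test. Exact power at 56 is 89.2% per endpoint, 9.2 percentage points above the printed 80%, and the exact minimum is 54. The printed pair is a normal-approximation result under an exact-test label. The error is conservative. Separately, no power is given for the both-endpoints rule; with each endpoint at 99% it is 79.5% to 89.2%.

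These figures assume one binary result per participant per endpoint and 56 participants analysed. Neither is secure in the text. Sections 6.1 and 7.2 take three ECGs from each participant, and no rule reduces them to one result. The denominator for diagnostic quality when no ECG is obtained is undefined, which is why joint power can be given only as a range. If the 60 completers of Section 11.1.3 are analysed, power is 87.9% per endpoint and 77.2% for both under independence, so under this test the extra four subjects lower power slightly.

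**What to change.** Keep the sample size and replace the power sentence in Section 10.1 with text such as:

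> With 56 evaluable subjects and one binary result per subject per endpoint, each exact one-sided test (0.025) is met with at most one failure (55/56; attained alpha 0.020). Power is 89.2% per endpoint at a true 99%. The probability of meeting both endpoints, each at 99%, is 79.5% (failures independent or never coinciding) to 89.2% (failures fully coincide). One failure is allowed at 54 to 69 evaluable subjects; at 53 none is allowed and per-endpoint power is 59%.

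Reconcile Section 11.1.3 (60 completers) with Section 4.3 (56), and quote the power for whichever number will be analysed. State how the three recordings become one result per participant, since the 55/56 pass mark depends on it.

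The cost is one rewritten paragraph in Section 10.1, one corrected sentence in Section 4.3 or 11.1.3, and one sentence defining the per-participant result. Restating 10.1 changes neither the sample size nor the conduct of the study.

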### 10.2 General Considerations

Continuous data will be presented by mean, standard deviation, median, minimum and maximum observation, and 95% confidence interval. Categorical data will be presented as frequencies, percentages, and the 95% Clopper-Pearson confidence interval. Significance tests will be conducted at a two-sided significance level (alpha) of 0.05, or a one-sided significance level of 0.025.

### 10.3 Participant Disposition

Participant disposition, including the total number of participants enrolled, randomized, and completed, along with reasons for early terminations, will be compiled.

### 10.4 Analyses

#### 10.4.1 Demographics and Baseline Characteristics

Participant demographics (age, sex, race/ethnicity) and descriptive characteristics will be summarized for all participants enrolled and for evaluable participants.

Document ID:	CC_TC_ECR_Intrepid 12Lead_2022_11549	Document title: Philips HeartStart Intrepid 12-lead ECG Study – The ICE study Protocol	Classification:	For internal use
Modified:	12SEP2022	Clinical Protocol	Author:	[name]
Version:	2.0		Approver:	Ref to Page 2
Status:	Final		Page:	41 of 51

### 10.4.2 Analysis of the Primary Endpoints

Endpoint 1A: Obtaining the 12-lead ECG

Endpoint 1B: Diagnostic quality of the 12-lead ECG tracings

A one-sided exact binomial test will be used to assess each of the primary endpoints. Both endpoints must be met for study success.

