## 5. STUDY PARTICIPANTS

### 5.1 Study Sample Considerations

The software change was created to help with high impedance experienced with some patients while obtaining a 12-lead ECG. This high impedance can be a result of skin conditions (wet skin) or electrodes that have been exposed to air for extended periods of time. Extended exposure to air will dry out the electrodes prematurely and reduce their adhesive and conductive properties. The study will utilize electrodes from an unopened package, a package open for 24 hours and package open for 30 days. This will be a stratification factor for randomization.

The inclusion/exclusion do not specify any clinical conditions for enrollment, as the study does not plan to diagnose or confirm any medical conditions.

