The Philips HeartStart Intrepid Monitor /Defibrillator is currently released for sale in the European market. It will be submitted to the FDA for 510(k) clearance during the time of this study. In the United States it is considered a Class II medical device. For the purposes of this study, the device will only be able to be used for monitoring and no clinical decision will be made based on the results obtained. None of the defibrillator accessories will be available for use. The Philips HeartStart Intrepid Monitor /Defibrillator used for this study is considered an investigational medical device. The sponsor considers this study to be a minimal risk study with a non-significant risk device. As monitor/defibrillator is not implantable, not supporting or sustaining life, not curing, mitigating, or treating disease, or otherwise preventing impairment of human health, and does not otherwise presents a potential for serious risk to the health, safety, or welfare of a subject.

A 12-lead ECG will be acquired three times (3) for each participant. The 12-lead ECG does not continuously record. As the leads are connected to the electrodes, markers will be placed for the three-lead and five-lead configurations. The Philips HeartStart Intrepid Monitor /Defibrillator has a 12-lead ECG preview screen that will allow the site staff to determine if a 12-lead ECG can be acquired. Once the 'start acquire' button is pushed, the recording will start and approximately 10 to 12 seconds a 12-lead ECG will be recorded. If the 12-lead does not have a good signal, no recording will be able to be obtained.

Participants will be randomized to electrodes that are either from an unopened package or have had the package open for 24 hours or 30 days. The 30-day electrodes will have a window of being opened plus or minus 10 days. The length of time the package is open is proportional to the amount of conductive gel that has dried on the electrode. The longer the electrode package is open, the drier the conductive gel and the higher the impedance. The dried electrodes will be used to simulate high impedance.

Document ID:	CC_TC_ECR_Intrepid 12Lead_2022_11549	Document title: Philips HeartStart Intrepid 12-lead ECG Study – The ICE study Protocol	Classification:	For internal use
Modified:	12SEP2022	Clinical Protocol	Author:	[name]
Version:	2.0		Approver:	Ref to Page 2
Status:	Final		Page:	27 of 51

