## 6.5 Measures to Minimize Bias

### 6.5.1 Type of Randomization

Block randomization will be employed to ensure balance across subjects with regard to electrode age (new, 24 hours, 30 days).

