### 10.4.4 Exploratory Analyses

Exploratory analyses are not planned.

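### The primary analysis pools all electrode ages, counts success after a swap to new electrodes and plans no result by electrode group, so study success does not show performance under high impedance

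*Combined protocol and SAP*

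**What the plan says.** Section 5.1 gives the reason for the study: "The software change was created to help with high impedance experienced with some patients while obtaining a 12-lead ECG". Section 6.1 uses dried electrodes to produce that condition and explains that "The length of time the package is open is proportional to the amount of conductive gel that has dried on the electrode". Section 6.5.1 makes electrode age the randomised factor: "Block randomization will be employed to ensure balance across subjects with regard to electrode age (new, 24 hours, 30 days". The allocation ratio is not stated.

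Section 10 does not use that factor. Section 10.1 sizes the trial for one overall proportion per endpoint: "Each hypothesized endpoint estimates a target proportion of 99% with an expectation to be statistically better than 90" per cent. Section 10.4.2 tests it the same way: "A one-sided exact binomial test will be used to assess each of the primary endpoints", and "Both endpoints must be met for study success". Section 10.4.4 adds "Exploratory analyses are not planned", and section 10.4.5 likewise plans no sensitivity analysis. Section 10.2 specifies 95% Clopper-Pearson intervals for categorical data but does not mention electrode group.

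Section 7.2 (Study Visit 1, 12-lead ECG) settles what counts as a failure of endpoint 1A. If no ECG can be obtained on 24-hour or 30-day electrodes, they are exchanged for electrodes from a fresh package. A fail is recorded only if the ECG still cannot be obtained.

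**The concern.** The design creates the contrast that would answer the study question, and the analysis then leaves it out. Two features work together. Pooling lets good results on new electrodes offset weaker results on dried ones. The replacement rule goes further: a participant whose dried electrodes gave nothing, and who then had an ECG on new ones, is a success for 1A. That participant's tracings for 1B also come from new electrodes.

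At stake is the claim made from a positive result. A reader would take success to mean that the updated software obtains a diagnostic ECG more than 90% of the time when impedance is high. The planned analysis would not establish that, and no planned table would show where the failures or the swaps occurred.

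**Working it through.** **Inputs.** From sections 3.2 and 10.1: null rate 0.90, target 0.99, one-sided alpha 0.025, 56 evaluable participants. Assumptions not in the plan: 1:1:1 allocation (about 19 on 30-day electrodes and 37 on the other two), the participant as the unit of analysis, and 99% success on new electrodes (the plan's own target).

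**1. The plan's figure.** "Using a one-sided exact test, with 80% power and alpha of 0.025, a sample size of 56 evaluable subjects is required". The one-sample normal approximation reproduces it:

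n = [(1.960·√(0.9·0.1) + 0.842·√(0.99·0.01)) / 0.09]² = 55.7, rounded up to 56.

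Exact rule at n = 56:
- P(at least 55 successes | 0.90) = 0.9^56 + 56·0.1·0.9^55 = 0.0198, so one failure passes.
- P(at least 54 | 0.90) = 0.072, so two failures do not.
- Power at 0.99 = 0.892.

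The sample size is sound for one pooled proportion.

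**2. Endpoint 1A as written, with swaps.** If aged electrodes work at first attempt with probability q and new ones with probability 0.99, the effective success rate in an aged group is q + (1 − q)·0.99.
- q = 0 in both aged groups: effective rate 0.99 everywhere, so P(1A met) = 0.892, identical to the planned power.
- 30-day q = 0.90, other groups at 0.99: effective 30-day rate 0.999. P(at most 1 failure) = 0.99^37·0.999^19·(1 + 37·0.01/0.99 + 19·0.001/0.999) = 0.94.

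The chance of meeting 1A hardly depends on how the dried electrodes perform.

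**3. Pooling alone, ignoring swaps.** Let p be the true 30-day rate. If the other 37 never fail, P(met) = p^19 + 19·(1 − p)·p^18. If they succeed 99% of the time, P(met) = 0.99^37·[p^19 + 19·(1 − p)·p^18] + 37·0.01·0.99^36·p^19.

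| True 30-day rate | Others at 99% | Others at 100% |
|---|---|---|
| 95% | 0.62 | 0.75 |
| 90% | 0.32 | 0.42 |
| 85% | 0.15 | 0.20 |
| 80% | 0.06 | 0.08 |
| 70% | 0.008 | 0.010 |

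For example, at 90% with the others at 100%: 0.135 + 19·0.1·0.150 = 0.42. These are probabilities for one endpoint; study success needs both.

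The unit is itself undefined, since three ECGs are taken per participant. If the 168 tracings were treated as independent, up to 9 failures would pass. The figures with the others at 99% would then be 0.86 at a 90% rate, 0.50 at 85% and 0.005 at 70%.

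**4. What the 30-day group can show.** When all n succeed, the two-sided 95% Clopper-Pearson lower limit is 0.025^(1/n).
- 19/19: 82.4%, one-sided p = 0.9^19 = 0.135.
- 18/19: lower limit 74.0%.
- Rejecting 90% within a group needs at least 36 participants with no failure (0.9^36 = 0.0225).
- Both aged groups together: 37/37 gives a lower limit of 90.5%, and 36/37 gives 85.8%.

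**The case against.** The strongest reply is that the trial was sized for a pooled claim and tests exactly that. The test is valid for the electrode mix, and replacing a dried electrode may be regarded as part of obtaining an ECG. Assignment is held in the database (section 6.5.2), and section 10.2 does not forbid a table by group. All of this is fair. It means that the pooled tests need not be dropped and that the gap is in specified reporting. It does not make the pooled result informative about dried electrodes.

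Three stronger readings are tempting, and the documents do not support them.

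- A reader might infer that pooling could hide a very poor 30-day group, because a pooled rate of 90% with no failures elsewhere corresponds to 1 − 0.10·56/19 = 70.5% in that group. That is the null boundary, not a rate likely to pass: without swaps the chance of meeting the endpoint there is about 0.012. With the participant as unit, a pass without swaps forces at least 18/19 observed successes on 30-day electrodes.
- A reader might infer that 24-hour electrodes carry about 1/30 of the stress, so that only about 19 of 56 participants face the challenge. Section 6.1 relates open time to dried gel but gives no impedance values, and the swap rule in section 7.2 treats both aged groups alike. The challenged group could be about 37.
- A reader might take 0.32 to 0.42 as the behaviour of 1A as written. Those figures isolate pooling and leave out the swap.

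**Conclusion.** The point holds. Section 10 tests one pooled proportion per endpoint and plans no result by the randomised factor, and the swap rule separates endpoint 1A from performance on the dried electrodes. Given 99% success on new electrodes and the participant as unit, 1A is met with probability 0.89 even if no aged electrode works at first attempt. Setting swaps aside and assuming 1:1:1 allocation, pooling alone lets one endpoint be met with probability 0.32 to 0.42 at a true 30-day rate of 90%, and 0.15 to 0.20 at 85%, with the other groups at 99% to 100%. It does not conceal a much lower rate.

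With about 19 participants per group, no outcome can support a rate above 90% on 30-day electrodes, so a pooled success cannot support that claim either. The pooled test remains valid for what it measures: performance over the mix of electrode ages, with replacement allowed.

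**What to change.** In section 10.4.2, keep the pooled tests and add:

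- 1A and 1B will be reported by randomised electrode group (new, 24 hours, 30 days) with the 95% Clopper-Pearson interval already named in section 10.2, based on the outcome with the assigned electrodes before any swap.
- The number swapped in each group, and the post-swap result, will be shown separately.
- Conclusions about high impedance rest on the pre-swap results in the aged-electrode groups. The pooled test supports only performance over the electrode mix with replacement allowed.

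State the unit of analysis for this table, and how 1B treats a participant who has no tracing before a swap. Amend section 10.4.4 to match.

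A table by group without the pre-swap outcome would not be enough, because it would credit ECGs from new electrodes to the 30-day group.

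The cost is some wording and one extra table, with no additional participants and no change to the visit. If the case report form does not already record the first-attempt result and the swap, it needs a field for each. The price is wide intervals, at about 19 per group, and a more modest claim about high impedance.
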